### 6.10.3 Biologic Correlates

Optional blood sample may be collected at the time of the FES PET scan procedure for determination of serum hormone levels (estradiol, estrone, follicle-stimulating hormone, sex hormone binding globulin, testosterone, free testosterone).

Patients participating in this study will have undergone clinical biopsy of the primary tumor and/or metastasis for which ER, PgR, and HER2 expression will be determined by IHC. Clinical records of these assays will be reviewed, and the assays themselves may be reviewed as needed.

On patients for whom archival biopsy material can be obtained, additional assays may be performed, and may include repeat and standardized ER, PR, and HER2 assays.

Patients with metastatic or recurrent disease may consent to optional research biopsies of the tumor performed at the baseline, i.e. prior to start of the selected endocrine targeted therapy, and after 1-12 weeks on therapy. Obtained tissues will be analyzed for a baseline expression and post-therapy changes in ER, PgR, HER2, AR, EGFR and VEGF using IHC methods. Some samples will be assayed for intra-tumor steroid hormone levels (estradiol, estrone, testosterone, dihydrotestosterone) using IHC and/or mass spectrometry techniques.

In some patients undergoing biopsy, a whole blood sample will be drawn during the same time point to allow correlation of steroid hormone levels in serum with levels in biopsy tissue.

Assays for ER and PgR will be read using the Allred scoring system, which provides a semi-quantitative and qualitative assessment of tumor expression levels (Harvey, 1999). IHC is the primary assay methodology for HER2. Scoring of HER2 is done by assessing intensity of the membranous stain (0, 1+, 2+, 3+). Scores of 0 and 1+ are considered negative and score of 3+ is considered positive. Score of 2+ is considered indeterminate and will be validated by fluorescence *in situ* hybridization

(FISH) (HER-2 DNA probe kit; Abbott Molecular Inc., Des Plaines, IL)(Yaziji, 2004). Analysis of HER2 will be done using information from the IHC assays and the FISH confirmation when required.

Measurement of these tumor-associated indices may enhance the predictive value of PET FES, provide information to better understand mechanisms of resistance to endocrine therapy, and eventually determine which patients are likely to appreciate clinical benefit as a result of endocrine therapy, even in the absence of an objective response.

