- 6.3.3.d** FES uptake predicted a greater likelihood of response to endocrine therapy. Patients with low or absent FES uptake were unlikely to manifest a response to treatment, yet FES did not help to distinguish which patients would experience a clinical benefit, defined as stable disease. Several factors may have contributed to this finding. Stable disease over 6 months included patients with disease that may have progressed slowly, independent of treatment, as well as patients with rapidly progressive disease in whom therapy slowed but did not abrogate tumor growth. The study was not designed to distinguish between these two outcomes. In addition, we identified PgR (progesterone receptor) expression as contributing to likelihood of response, and noted that elevated estradiol levels and HER2 expression were associated with non-response. In this new study we propose to document tumor characteristics including quantitative ER mRNA levels measured by PCR and semi-quantitative levels of ER, PgR, AR and HER2 by IHC. Gathering these indices as part of the proposed study may help to enhance the predictive value of PET FES, allow understanding of mechanism of resistance to endocrine therapy, and potentially determine which patients are likely to appreciate clinical benefit as a result of endocrine therapy, even in the absence of an objective response.
- 6.3.3.e** In prior observational imaging trials (unpublished data) we have measured regional estrogen-ER binding using FES PET before and after treatment with estrogen depleting therapies, Aromatase inhibitors (AI), and estrogen blocking therapies, Tamoxifen (TAM), or fulvestrant (FUL) in 30 metastatic breast cancer patients. As expected, tumor FES uptake declined markedly on ER blockers TAM and FUL (average 54% decline), but less than 15% on average on estrogen-depleting AIs ( $p < 0.001$ ). All 5/5 patients taking TAM showed complete tumor blockade (FES SUV ≤ 1.5 after treatment), compared to 4/11 of FUL patients ( $p = 0.009$ ). We concluded that molecular imaging can assess the *in vivo* pharmacodynamics of targeted agents, and may give insight into the activity of established therapeutic agents.

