## **6.14 STATISTICAL CONSIDERATIONS**

### **6.14.1 Analysis Plan**

The primary application will be pilot studies with enrollment of about 20 patients, in which the in vivo effects of endocrine-targeted therapy are measured by serial FES PET. The primary endpoints will be quantitative and qualitative measures of FES uptake, and measures of change in FES uptake (Section 6.10.2). Additionally, patients will be followed for disease progression. Associations among FES and FDG PET measures, progression, and biological correlates (Section 6.10.3) may be examined in descriptive analyses.

An expected primary analysis is to examine whether FES uptake changed on average between serial assessments. This may be assessed by a one-sample test of the percent change in FES SUV. For example, a one-sided test at the 0.05 level of significance could evaluate whether the average

percent change in FES SUV was greater than 20%, considered a biologically significant change. In serial FES SUV measurements of heavily-pretreated breast cancer patients, change in FES SUV was approximately normally distributed with a standard deviation of about 25 percentage points, for both patients treated with blocking therapy (tamoxifen or fulvestrant) or non-blocking therapy (aromatase inhibitor). Using this standard deviation and n=20 to test whether the average change was greater than 20%, the power would be 0.97 if the true change is 40%, and 0.85 if the true change is 35%. To conclude only that the average percentage change was different from zero (using a two-sided test at the 0.05 level of significance), power would be 0.95 to detect a true average change of 20% (and 0.85 if the true standard deviation were 30 percentage points).

Other analyses for pilot studies could examine what proportion of patients experienced a threshold in percentage change, or surpassed a targeted follow-up FES SUV value. These percentages will be reported using a 90% Wilson score binomial confidence interval (Agresti, 1998). Width of these confidence intervals for pilot studies of n=20, n=25, and n=30 are given in Table 6.3 for a range of observed percentages.

**Table 6.3:** 90% Wilson score binomial confidence intervals (CIs) by percent observed and sample size.

observed percentage (CI) for n=20	observed percentage (CI) for n=25	observed percentage (CI) for n=30
0.1 (0.03, 0.26)	0.12 (0.05, 0.27)	0.1 (0.04, 0.23)
0.2 (0.09, 0.38)	0.20 (0.10, 0.36)	0.2 (0.11, 0.34)

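### Section 6.10.3 reads ER and PgR, including paired change, only by a semi-quantitative score that can miss a modest fall, and drops the ER mRNA assay of 6.3.3.d

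*Combined protocol and SAP*

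**What the plan says.** - **Tissue change is planned.** On the optional paired biopsies, section 6.10.3 says: "Obtained tissues will be analyzed for a baseline expression and post-therapy changes in ER, PgR, HER2, AR, EGFR and VEGF using IHC methods".
- **Reading method.** For the two hormone receptors the same section says: "Assays for ER and PgR will be read using the Allred scoring system, which provides a semi-quantitative and qualitative assessment of tumor expression levels". It gives no category limits, names no continuous readout, and does not say whether readers know which biopsy came first.
- **A quantitative ER assay is proposed elsewhere.** Section 6.3.3.d intends to document "quantitative ER mRNA levels measured by PCR and semi-quantitative levels of ER, PgR, AR and HER2 by IHC". Section 6.10.3 does not list the PCR assay. Table 6.2 has no row for it; footnote 4 only allows further pathology tests in some patients.
- **The FES side is continuous.** Section 6.10.2.a defines change as a percentage and as SUV units. The example test in 6.14.1 asks whether the average "percent change in FES SUV was greater than 20%, considered a biologically significant change".
- **Status of the comparison.** Section 6.2.2 makes correlation of FES uptake with histopathology a secondary objective, where the regimen makes it relevant. Section 6.14.1 treats associations with the biological correlates as possible descriptive analyses.

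**The concern.** A continuous percent change in FES SUV is to be set against change in an ordinal score. Eligibility requires ER-positive disease (6.4.1.b), so some tumours may start in the top band of the scale, where a band can hide a real decline.

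Sections 6.2.1 and 6.3.3 name two effects of treatment, on ER expression and on estradiol binding. When FES uptake falls and tissue ER looks stable, the natural reading is blocked binding. That reading is only as good as the tissue measure's ability to show a fall had there been one. With a banded score, partial loss of ER and pure blockade can look the same. The optional biopsies could then yield less than the slides contain.

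The mRNA assay would supply a quantitative ER measure, but as written it has no specimen, time point or analysis. For PgR, no quantitative measure is described anywhere.

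**Working it through.** **1. The plan's own figures around 20%.** Inputs from 6.14.1: n = 20, SD 25 percentage points (30 as a sensitivity value), level 0.05. Formula: power = Φ(δ/(SD/√n) − z).

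| Test | δ/(SD/√n) | z | Power | Stated |
|---|---|---|---|---|
| true 40% against 20%, one-sided | 20/5.590 = 3.578 | 1.645 | 0.973 | 0.97 |
| true 35% against 20%, one-sided | 15/5.590 = 2.683 | 1.645 | 0.850 | 0.85 |
| true 20% against 0, two-sided | 3.578 | 1.960 | 0.947 | 0.95 |
| same, SD 30 | 20/6.708 = 2.981 | 1.960 | 0.846 | 0.85 |

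All four reproduce under the normal approximation. They concern mean FES SUV change and say nothing about tissue. The documents give no figure for the resolution of the Allred score.

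**2. How often a banded score misses a 20% relative fall.** Assumptions, none of them in the documents: the score has a stained-cell proportion part whose top band runs from c to 100%; baselines are spread evenly over that band; staining intensity is ignored. A tumour at baseline p falls to p(1 − f). It leaves the top band if p ≤ c/(1 − f). The share keeping the same proportion score is 1 − [min(1, c/(1 − f)) − c]/(1 − c). With f = 0.20:

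| c | c/0.8 | Share registering | Share unchanged |
|---|---|---|---|
| 50% | 62.5% | 12.5/50 = 25% | 75% |
| 67% (two-thirds) | 83.3% | 16.7/33.3 = 50% | 50% |
| 75% | 93.8% | 18.75/25 = 75% | 25% |
| 90% | above 100% | 100% | 0% |

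**3. Sensitivity to baseline, c two-thirds, f = 0.20.** Baselines 70–100%: registering (83.3 − 70)/30 = 44%, unchanged 56%. Baselines 80–100%: registering (83.3 − 80)/20 = 17%, unchanged 83%.

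**4. Larger falls.** Every tumour leaves the top band once f ≥ 1 − c. At c two-thirds that is any fall of one third or more, so falls of 35%, 40% and 54% are all registered. At c = 50%, a 35% fall is registered by (76.9 − 50)/50 = 54%, a 40% fall by (83.3 − 50)/50 = 67%, and a 54% fall by all. The 54% is the average FES decline on ER blockers in 6.3.3.e, used here only as a reference size.

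**5. Correlation of scored with true change.** Simulation with two-thirds as the top limit, assumed lower limits of 0, 1%, 10% and one third, and baselines 70–100%: about 0.63 when the relative fall has mean 15% and SD 15%; about 0.80 with mean 20% and SD 25%; about 0.82 with mean 35% and SD 25%. The SD of 25 borrows the plan's FES value; the SD of 15 has no source in the documents.

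**The case against.** A reader might infer that the Allred score cannot register a 20% fall in a strongly positive tumour. The documents do not support that. They give no band limits, and under the assumed limits between 25% and 100% of top-band tumours do register it. Intensity is also left out: a drop in intensity would lower the total score even where the proportion band holds. This objection stands, and only *can fail to register* is defensible.

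A reader might also infer that the biopsies would show no change where FES shows a change that the plan calls biologically significant. The 20% in 6.14.1 applies to the average percent change in FES SUV across patients. No section sets it for stained cells in one tumour or says that the two change one for one. Stable tissue ER with falling FES is also what receptor blockade would produce, so it is not in itself an assay failure.

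Nor is tissue the only check on the primary objective. Section 6.2.1 measures that by serial PET alone, 6.3.3.a words the hypothesis as expression and/or binding, and section 6.1 accepts that some studies may have no pathologic correlate.

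Finally, 6.3.3.d does mention ER mRNA, and 6.10.3 and the calendar leave room for extra assays. So *only* holds for what 6.10.3 specifies, not for the whole protocol. Allred is a cited method that the plan openly calls semi-quantitative.

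What remains is that no continuous ER or PgR stain readout is specified for paired change, and that the mRNA assay is proposed in one section and absent from the section that defines the assays.

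**Conclusion.** The point holds as an inexpensive improvement to a secondary correlate. Section 6.10.3 specifies a semi-quantitative score for ER and PgR change that will be compared with a continuous FES measure, and it does not carry forward the quantitative ER assay of 6.3.3.d.

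For a 20% relative fall, between none and three quarters of top-band tumours would keep their proportion score, as the assumed lower limit moves from 90% to 50%. This rests on the assumed limits, on even baselines and on ignoring intensity, so the unchanged share for the full score would be smaller wherever intensity also drops. Falls above one third are always registered at the two-thirds limit. With changes as variable as the plan expects for FES, scored and true change still correlate at about 0.8. The loss is therefore concentrated in modest falls.

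The primary FES analysis and its power are unaffected. No tissue endpoint is powered, and the biopsies are optional.

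**What to change.** In 6.10.3:

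1. Keep the Allred score for classifying ER and PgR.
2. From the same slides, also record the percentage of positive cells and the percentage at each staining intensity.
3. Name the resulting continuous measure as the one used for correlation with FES SUV and for paired ER and PgR change.
4. State that each patient's two biopsies are read blind to time point. Section 6.10.2.b already blinds the FES observers to clinical data.

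Then reconcile 6.3.3.d with 6.10.3 on ER mRNA: either give the assay a specimen, time point and descriptive analysis in 6.10.3 and the calendar, or remove it from 6.3.3.d.

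The cost is a few extra data fields and slightly more reading time. Items 1 to 4 need no new tissue or assay. Keeping the mRNA assay would need laboratory work that the plan does not yet describe; removing it is a text edit.

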## 6.11 STUDY CALENDAR

Baseline evaluations are to be conducted prior to administration of protocol therapy, typically within 30 days. Baseline FDG PET/CT scan will be obtained near the time of the [F]FES-PET/CT scan, typically within 14 days. Procedures are outlined below in Table 6.2.

**Table 6.2. Study Calendar.**

	Pre-Study	Imaging 1	Rx 1	Imaging 2 	Rx 2	Imaging 3 	Follow up
Informed Consent	X						
Demographics	X						
Pregnancy Test 	X						
Vital Signs 		X		X		X	
Research lab tests 		X		X		X	
ER, PgR, HER2 	X						
FDG PET/CT 	X			X		X	
[  F]FES injection and PET 		X		X		X	
Collect serum hormone levels 		X		X		X	
Adverse Event Evaluation		X (0-24hr)		X (0-24hr)		X (0-24hr)	
Optional tumor tissue biopsy and blood draw 		X		X			

 If patient is pre-menopausal, and birth control use is not confirmed

 Vital signs include heart rate and blood pressure

 Additional blood tests to measure hormone levels (e.g. estradiol, estrone, testosterone, DHT, SHBG) or other hormone related measures might be performed in some patients depending on the treatment regimen.

 Pathology results from primary or metastatic biopsy will be reviewed and additional pathology tests may be performed on some patients depending on the treatment regimen.

 FES PET/CT and FDG PET/CT will be done at 1-12 weeks after the Imaging 1 time point depending on the treatment regimen.

 Repeat FDG PET may be omitted in patients on SERD therapies.

 FES PET/CT and FDG PET/CT may be done at 1-12 weeks after the Imaging 2 time point depending on the treatment regimen.

 Optional blood sample for estradiol, estrone, follicle-stimulating hormone, sex hormone binding globulin, testosterone and free testosterone serum levels.

 In patients consented to optional biopsies, obtain metastatic or recurrent tumor tissue from an FDG and/or FES avid site after completion of PET imaging but prior to start of the endocrine targeted therapy. Repeat the biopsy from the same site after 1-12 weeks on treatment. (Where available and medically appropriate, a clinical or research biopsy that involved sampling of a relevant lesion within 6 months prior to the enrollment may be utilized in place of the baseline optional biopsy.) A blood draw done during the same time point will accompany some biopsies.

## **6.12 MEASUREMENT OF EFFECT**

For the purposes of this study, the outcome measured will be the change in FES and FDG PET measures between the serial sets of scans. Response evaluations will not be evaluated as part of this study, though the information may be recorded if it is collected for treatment studies the patient may be participating. Patients may also be followed for up to 20 years for disease progression and overall survival.

### **6.12.1 Time to Progression**

Time to progression (and progression-free survival) will be measured as the time from the start of endocrine therapy to the time the patient is first recorded as having disease progression. If a patient never progresses while being followed, the patient will be censored at the time he/she terminates follow-up or by date of disease progression or death.

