will be recorded. A known quantity of nonradioactive FES will be added to plasma (from blood collected prior to injection) to determine binding to sex steroid binding protein (SBP). For patients in whom a second venous access line is feasible and has been placed, venous blood samples may be collected at 5, 20 and 60 minutes after injection of the [F]FES for metabolite analysis in selected patients. Heart rate and blood pressure will be measured after the FES injection.

**6.6.2.c After the [F]FES PET Scan:** A follow up phone call will be made by study staff within 24 hours after the FES PET scan to ask about any signs of adverse effects. Patients will typically start the selected hormone targeted therapy within 30 days of the FES PET scan. Patients who have started aromatase inhibitors prior to [F]FES PET will be permitted to enter the study, if an additional endocrine targeted treatment is planned.

**6.6.2.d** In patients who consent to optional biopsies, a baseline tumor sample will be obtained after completion of the baseline PET imaging but prior to starting the selected endocrine targeted therapy. Where available and medically appropriate, a clinical or research biopsy that involved sampling of a relevant lesion within 6 months prior to the enrollment may be utilized in place of the baseline optional biopsy.

In some patients undergoing biopsies, a whole blood sample will be collected prior to starting the therapy, to allow correlation of steroid hormone levels in serum and biopsy tissue.

**6.6.2.e Repeat FES PET scan and FDG PET scan :** Patients will undergo a second FES PET and FDG PET scan after starting endocrine targeted therapy to assess the effect of therapy on ER expression and estradiol binding to the receptor. Exact timing of the second FES and FDG scans, will depend upon the endocrine targeted regimen and dosing, but typically will be 1 – 12 weeks after starting therapy.

The repeat FDG PET may be omitted in patients on SERD therapies, where repeat FES PET is used primarily to evaluate residual ER availability rather than tumor response. This will be determined by requirements of the co-enrolling companion therapeutic protocol.

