**6.6.2.f** In patients who consent to optional biopsies, an early response tumor sample will be obtained 1-12 weeks after starting the selected therapy. This biopsy should take place after completion of the repeat PET imaging and should target the same tumor site as the baseline biopsy. A whole blood sample may be drawn for correlation of steroid hormone levels in serum and biopsy tissue.

**6.6.2.g Week 1 to 20 years after [F]FES PET Scan:** Clinical follow-up will continue for up to 20 years, time of progression and date of death will be

recorded. For some patients, especially those receiving two endocrine-directed treatments, a third FES PET scan and additional research FDG PET scan may also be obtained 1-12 weeks after the second FES PET scan. For each patient, a maximum of 3 FES PET and 3 FDG PET scans would be done.

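### Section 6.12.1 censors patients without progression at end of follow-up or death, not at the last disease assessment, so unassessed time can count as progression-free

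*Combined protocol and SAP*

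**What the plan says.** Section 6.12.1 gives one definition for TTP and progression-free survival: "the time from the start of endocrine therapy to the time the patient is first recorded as having disease progression". For a patient who does not progress, "the patient will be censored at the time he/she terminates follow-up or by date of disease progression or death". No section names the last disease assessment as a censoring date.

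On follow-up:

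- Section 6.12: "Patients may also be followed for up to 20 years for disease progression and overall survival".
- Section 6.6.2.g: "Clinical follow-up will continue for up to 20 years, time of progression and date of death will be" recorded. No assessment interval or method is given.
- Section 6.12: "Response evaluations will not be evaluated as part of this study". Response data may be recorded if a treatment study collects them.
- Section 6.6.2.g, on study imaging: "a maximum of 3 FES PET and 3 FDG PET scans would be done". Section 6.6.2 places the repeat scans 1-12 weeks after starting therapy and 1-12 weeks after the second scan.
- Table 6.2 has no entry in its Follow up column.

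On use, Section 6.10.2.c says FES uptake will be compared with TTP. Section 6.14.1 makes FES uptake and its change the primary endpoints and puts associations with progression among descriptive analyses that may be done.

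**The concern.** A patient is under observation for progression only while someone is looking for it. Once the study scans are over, looking depends on routine care or on a companion treatment protocol. The study may still keep the patient under follow-up for survival. The written rule leaves that patient in the risk set, progression-free, until follow-up ends or the patient dies.

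For example, a patient last assessed at month 6 and followed for survival to month 24 contributes 24 months of progression-free time, of which 24 − 6 = 18 were unobserved. Extra time at risk without the possibility of a recorded event lowers the estimated progression rate and lengthens the Kaplan-Meier median.

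At stake is the descriptive TTP estimate and what is read from it. The Schema (Section 6.1) says that promising data from this study will be used to design a multi-center phase II trial.

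**Working it through.** **1. The plan's own figures.** The plan states no figure for TTP. Its only power calculation is the one-sample test of percent change in FES SUV at n = 20 (Section 6.14.1). With power = Φ(δ/(SD/√n) − z):

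- Against 20%, one-sided 0.05, SD 25, true change 40% (δ = 20): Φ(3.578 − 1.645) = 0.97.
- The same with true change 35% (δ = 15): Φ(2.683 − 1.645) = 0.85.
- Against zero, two-sided 0.05, δ = 20, SD 25: Φ(3.578 − 1.960) = 0.95.
- The same with SD 30: Φ(2.981 − 1.960) = 0.85.

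All four match the stated values, and none depends on the censoring rule.

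**2. Reading the rule.** Three censoring dates are offered for a never-progressor: end of follow-up, progression and death. The second is impossible by definition. It has no numerical effect, because anyone with that date is already an event. The other two are not tied to a disease assessment.

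**3. Illustration of size.** The documents give no TTP rate, assessment interval or follow-up gap, so every input here is an assumption: exponential TTP with true median 9 or 12 months; a share of patients whose checks stop at a time uniform on 2-8 months, after which progression is never recorded; survival after progression exponential with median 18 months; follow-up to 60 months or death. Kaplan-Meier medians (months) come from large simulations; a range shows the spread over repeated runs.

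| Share losing checks | Written rule, true 9 | Written rule, true 12 |
|---|---|---|
| 2% | 9.1 | 12.1-12.2 |
| 5% | 9.2 | 12.4-12.5 |
| 10% | 9.5-9.6 | 13.0 |
| 20% | 10.2-10.3 | 14.2-14.3 |
| 30% | 11.2-11.3 | 15.9-16.1 |

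Censoring at the last assessment returns 9.0 and 12.0 throughout. If follow-up instead ends 3 months after the last check, shares of 10-30% give only 9.3-10.1 and 12.3-13.1 under the written rule.

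**4. A second set of assumptions.** Checks are about weekly until a stop uniform on 3-24 months for every patient, followed by an unassessed gap. With a true median of 12 (49% censored), the median is 12.0 when censored at the last assessment, and 13.75, 15.5 and 18.25 after gaps of 3, 6 and 12 months. With a true median of 6 (27% censored), it is 6.25 against 6.5 for all three gaps. The direction is the same, but the size depends heavily on the inputs.

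**5. Scale against sampling error.** For an uncensored exponential sample, the standard error of the median is about m/(ln 2 × √n). At n = 20 this is 9/(0.693 × 4.472) = 2.9 months and 12/(0.693 × 4.472) = 3.9 months. Every shift in the step 3 table is within one standard error except 30% at a true median of 12, where the shift is about 4.

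**6. Can the rule create an association?** Take two groups with the same true TTP, one with 30% losing checks and one with none, on the inputs of step 3. The written rule gives a progression-rate ratio of about 0.60 where the truth is 1. This requires loss of checks to differ between the groups. If it is the same at every level of FES uptake, this mechanism does not arise.

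**The case against.** The strongest reply is that the scenario is not in the documents. Section 6.12 describes a single follow-up for progression and survival together, Section 6.6.2.g records both, and eligibility (6.4.1.g) requires access to records on response and long-term follow-up. If progression is followed until follow-up ends, the two censoring dates nearly coincide. Besides, no test, power figure or decision rests on TTP, and the shifts are mostly smaller than the sampling error of a 20-patient pilot. All of this stands and limits the point. It does not remove it: the rule as written does not require the dates to coincide, and a bias does not become acceptable because it is smaller than the noise.

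It also stands that the exact recovery of 9.0 and 12.0 in the illustration follows from letting checks stop independently of progression risk. If checks stop because a patient is deteriorating, censoring at the last assessment is informative too.

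Three stronger readings are tempting and are not supported:

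- *TTP is overstated.* A reader might take this as fact. It is conditional on gaps between last assessment and end of follow-up that the documents neither show nor exclude.
- *The FES-TTP association is confounded by scan frequency.* A reader might infer this because care inside and outside companion trials may differ. The documents do not say that assessment intensity varies with FES uptake, and without that the distortion in step 6 does not follow.
- *Patients already on an aromatase inhibitor are credited with time before enrolment.* Section 6.6.2.c says such patients "will be permitted to enter the study, if an additional endocrine targeted treatment is planned", so the literal start of endocrine therapy could predate entry. But the Schema and Section 6.6.2.c describe starting the chosen regimen after baseline imaging, and that regimen is the natural reading of the start date. The wording needs clarifying; it is not shown to be an error.

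**Conclusion.** The point holds in a limited form. The censoring sentence in Section 6.12.1 contains an impossible date and, followed literally, counts unassessed time as progression-free. The direction of any resulting bias in TTP is upward.

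Its size cannot be derived from the documents. On the main set of assumptions, with 2-30% of patients losing checks at 2-8 months, it runs from about 0.1 to 2.3 months on a true median of 9 and from about 0.1 to 4 months on a true median of 12. It is nil when follow-up ends at the last assessment. Because TTP serves descriptive analyses only, the primary analysis is untouched. The correction is worth making because it is cheap and because the last assessment date may be hard to reconstruct years later.

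**What to change.** Replace the censoring sentence in Section 6.12.1 with: *A patient without recorded progression is censored at the last disease assessment documented as free of progression.* Record that date at each follow-up update.

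As a clarification only, state that the clock starts at the first dose of the endocrine regimen selected for this study, after the baseline FES PET.

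The cost is two sentences and one more data field, taken from clinical records to which patients already agree to give access. Imaging, treatment and sample size do not change. The downsides are shorter censored times, somewhat less person-time, and the possibility of informative censoring if checks stop because of deterioration. Recording why assessments stopped, where the notes say so, would let a reader judge that.

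This change concerns the censoring date for TTP. Whether death counts as an event for progression-free survival, which shares the definition, is a separate question that it does not settle.
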